10.3 Accrual goal

It is expected that 20 subjects will be enrolled in the trial each year. To meet the accrual goals of 47, we require approximately 2.5 years of enrollment with 2 years of follow up.

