10.4 Stopping rule

Serious adverse events and deaths will be reviewed by the study team and principal investigators on an ongoing basis.

The risk of treatment-related mortality is 10-20% in patients with steroid refractory chronic GVHD (15, 42). The study will have continuous mortality monitoring, and if $\geq 20\%$ have treatment-related mortality that is possibly, probably or definitely related to the study drug, accrual will be halted (see stopping rules below). Subjects, who are already enrolled in the study, and are tolerating the study drug may continue the drug at the discretion of the treating physician.

Continuous monitoring (43) will be performed after each subject has received the first dose of ruxolitinib, beginning when the 2nd subject has received the first dose of ruxolitinib, with K=47 interim analyses, a null hypothesis mortality rate of 0.10, an alternative hypothesis of 0.20, and power of 0.80. The sample size is too small to control alpha and power simultaneously, so alpha is 0.19 to allow for 80% power (see below table for operating characteristics). The table below displays the boundaries b_k for each interim analysis k. If the observed number of treatment-related mortality is greater than b_k , accrual will be terminated. Stopping boundaries were calculated with the R package “clinfun” based on Ivanova (41), using this code: toxbdry(0.1, 0.2, 3:47, cP0=0.1, cP1=0.8, priority="alt").

Continuous monitoring boundaries for K=47 when the true mortality rate is 0.10 and the alternative hypothesis is 0.20 and alpha=0.05, 80% power

Stop if treatment-related mortality is greater than or equal to the boundary ($\geq b_k$)

K	1	2	3	4	5	6	7	8	9	10	11	12	13	14	15	16	17	18	19	20	21	22	23
b_k	-	2	2	2	2	2	2	2	2	3	3	3	3	3	4	4	4	4	4	4	4	4	5

K	24	25	26	27	28	29	30	31	32	33	34	35	36	37	38	39	40	41	42	43
b_k	5	5	5	5	5	5	6	6	6	6	6	6	6	6	7	7	7	7	7	7

K	44	45	46	47
b _k	7	8	8	9

Operating characteristics of the stopping rule

P(death)	P(stopping)	Expected sample size
0.10	0.192	41.1
0.12	0.309	37.8
0.14	0.443	34.1
0.16	0.577	30.2
0.18	0.697	26.4
0.20	0.795	22.9

All grade 3 and above or serious adverse events recorded during the study will be summarized. Listings of deaths, serious adverse events, and adverse events leading to early termination of study treatment or premature withdrawal from study will also be provided to the DSMC.

Section 11.0 Records to be Kept

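### The mortality rule counts subjects from their first dose, but its stated 80% chance of stopping assumes every outcome is known at once; with follow-up lag that figure is not supported unless deaths come early and the at-or-above reading applies

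*Combined protocol and SAP*

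**What the plan says.** Section 10.4 (Stopping rule) describes the looks this way: "Continuous monitoring (43) will be performed after each subject has received the first dose of ruxolitinib". They start with the second subject, "with K=47 interim analyses, a null hypothesis mortality rate of 0.10, an alternative hypothesis of 0.20, and power of 0.80". Deaths are compared with a boundary b_k, where k is the number of subjects dosed. The section accepts a raised type I error, "so alpha is 0.19 to allow for 80% power". The boundary comes from a call that begins "toxbdry(0.1, 0.2, 3:47, cP0=0.1, cP1=0.8", which has no accrual or follow-up input. The last row of the operating-characteristics table reads "0.20 0.795 22.9": mortality rate, stop probability, expected sample size.

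The direction of the rule is given in two ways. The text says "If the observed number of treatment-related mortality is greater than b_k", while the table heading says "Stop if treatment-related mortality is greater than or equal to the boundary". A crossing halts accrual; subjects already enrolled may continue.

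Section 10.4 gives no period within which a death counts and no minimum follow-up before a subject enters k. Section 5.1 sets treatment at 6 months, extendable to 12. Section 9.0 follows toxicity to 30 days after the last dose. Section 10.3 gives the pace: "It is expected that 20 subjects will be enrolled in the trial each year".

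**The concern.** A sequential binomial boundary has its calculated properties only if each subject's outcome is known when that subject is added to the denominator. Here a subject dosed today enters k as though already a survivor, while treatment-related death can occur months later. The denominator runs ahead of the deaths, so the boundary is crossed later, or not before the 47th subject is dosed. Because a crossing acts only on accrual, a crossing after the 47th dose changes nothing.

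At stake is the plan's only numerical mortality boundary. Those overseeing the trial are told that it halts accrual with about 80% probability if true treatment-related mortality is 20%, after about 23 subjects on average. If the true probability is lower, more subjects are dosed before a halt than the plan indicates.

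**Working it through.** **Inputs.** From 10.4: p0 = 0.10, p1 = 0.20, 47 subjects, the printed b_k, and stated stop probabilities of 0.192 (expected N 41.1) and 0.795 (expected N 22.9). From 10.3: 20 subjects per year. From 5.1 and 9.0: 6 to 12 months of treatment plus 30 days. Assumed, because the documents are silent: when deaths occur after the first dose.

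**Step 1: reproduce the stated figures with no lag.** Let q_k(x) be the probability of x deaths among the first k subjects with no earlier crossing. Then q_k(x) = (1−p)·q_{k−1}(x) + p·q_{k−1}(x−1). States that cross the boundary are removed at each k, and P(stop) is the total removed.

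| Boundary, outcomes known at once | P(stop) at 10% (expected N) | P(stop) at 20% (expected N) |
|---|---|---|
| Stated in 10.4 | 0.192 (41.1) | 0.795 (22.9) |
| Printed b_k, stop if ≥ | 0.366 (34.6) | 0.896 (15.9) |
| Printed b_k, stop if > | 0.149 (42.9) | 0.762 (25.6) |
| Reconstructed boundary, looks 3 to 47 | 0.190 (41.1) | 0.795 (22.9) |

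The printed boundary does not give the stated table under either reading. The reconstruction stops when deaths exceed the 1−c quantile of Binomial(k, 0.10), with c = 0.0757 found by search. It matches the stated figures almost exactly, with no lag. The R package named in 10.4 was not available, so this boundary is an inference about how the table was produced.

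**Step 2: size of the lag.** Subjects dosed within a window of w months number (20/12)·w.
- w = 6: 20/12 × 6 = 10.
- w = 7 (6 months plus about 30 days): 20/12 × 7 = 11.7, about 12.

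If deaths are uniform over the window, the expected number not yet seen at 20% mortality is (20/12)·w·0.20/2. That is 1.0 at 6 months, 1.2 at 7 and 2.0 at 12, against printed boundary values of 2 to 9. These windows are not long: the table in 5.4 places the end-of-therapy safety evaluation at 8 months, or 14 months with extended treatment and taper.

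**Step 3: stop probability with lag.** Simulated trials used Poisson accrual at 20 per year and 47 subjects. Deaths were uniform over the window, and looks were taken at each first dose with k = number dosed. Results vary by about 0.01 between runs. P(stop) at 20% mortality:

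| Deaths uniform over | Printed, ≥ | Printed, > | Reconstructed |
|---|---|---|---|
| No lag (exact) | 0.896 | 0.762 | 0.795 |
| 3 months | 0.83 | 0.66 | 0.69 |
| 6 months | 0.76 | 0.58 | 0.62 |
| 7 months | 0.74 | 0.55 | not run |
| 12 months | 0.60 | 0.40 | 0.44 |

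At 6 months the mean number dosed is 27.3 (≥), 35.4 (>) and about 34 (reconstructed), against the stated 22.9. For the reconstructed boundary, P(stop) at 10% mortality falls from 0.19 to about 0.08.

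**The case against.** **Death timing is assumed.** This stands. A reader might infer that the rule definitely fails to deliver 80%. The documents do not support that: with the at-or-above reading and deaths within 3 months, P(stop) is still about 0.83. With front-loaded deaths inside 7 months and a check at every death, it is about 0.82.

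**Deaths are already watched continuously.** A reader might infer that a death between dosings goes unexamined. Section 10.4 says deaths are reviewed on an ongoing basis, Section 9.2.3 requires serious adverse events to reach the manufacturer within 24 hours, and Section 9.0 sends deaths within 30 days of treatment to the data and safety monitoring committee. A check at each death is a reasonable reading. It recovers little, because k still counts everyone dosed: at 7 months about 0.76 to 0.77 (≥) or 0.59 (>), against 0.74 and 0.55.

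**Part of the shortfall is not lag.** Correct. Under the strictly-above reading the no-lag value is already 0.762, so only the further fall to 0.58 at 6 months is due to lag. Under at-or-above, the drop from 0.896 starts from a figure that the plan never claims; against the stated 0.795 the gap at 7 months is about 0.06 (0.795 − 0.74).

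**About 12 outstanding subjects cannot apply at every look.** Correct. At k = 2 to 11 there are fewer than 12 subjects in total. The count of 10 to 12 holds once accrual is established.

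**Conclusion.** The defect holds. Section 10.4 fixes k by first doses, states no mortality window, and reports operating characteristics that match immediate outcomes. Lag lowers the stop probability under every boundary reading. For evenly spread deaths and looks at first doses, all three boundaries fall below 0.795 once the spread reaches 6 months (0.76, 0.58 and 0.62). The exception is early deaths combined with the at-or-above reading. The plan commits to neither condition, so its 80% is unsupported rather than shown to be false. The size rests on the assumed death timing, on accrual at 20 per year and, for the reconstructed column, on an inferred boundary. The change should be made, as the rule governs when accrual halts for mortality.

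**What to change.** In 10.4, in this order:

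1. Reconcile the boundary: strictly-above versus at-or-above, alpha 0.19 in the text versus 0.05 in the table title, and a start at the second subject versus looks 3 to 47 in the code.
2. State the window in which a treatment-related death counts.
3. Define k by follow-up, for example deaths plus the summed fraction of the window completed by survivors. Check the boundary at each treatment-related death as well as at each first dose.
4. Recalculate b_k and the operating-characteristics table by simulation at 20 subjects per year. Report stop probabilities at 10% and 20% against the intended 0.19 and 0.80.

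The order matters. Fractional k on the printed table read as at-or-above gives about 0.88 at 20% but about 0.36 at 10%, nearly double the stated 0.192. Read as strictly-above, it gives only about 0.72 at 20% (7-month window). Counting only subjects who have died or completed the window restores the no-lag probabilities, but more are dosed before a stop: about 24.6 on average against 15.9 (printed, ≥, 6-month window, 20% mortality).

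The cost is revised wording and a short simulation, with no extra patients. The downsides are that k must be computed from follow-up time at each look, and the restated figures may be less favourable than those now printed.

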Chronic graft-versus-host-disease (GVHD) is a major complication of allogeneic hematopoietic cell transplant that impairs quality of life, and is associated with significant morbidity and mortality. Management of chronic GVHD with prednisone is associated with an overall response rate of approximately 60%, and a complete response rate of approximately 30% but sclerotic features do not respond as well. Based on the biology of chronic GVHD and available preliminary evidence, we hypothesize that ruxolitinib will be effective in the management of sclerotic chronic GVHD. The study is an open label, phase II multicenter trial designed to evaluate the efficacy of ruxolitinib as a salvage treatment for subjects with sclerotic GVHD (sclerosis or fasciitis). The primary objective is to determine the proportion of subjects with response rate (complete and partial responses) in skin and/or joint, as determined by 2014 NIH consensus criteria, at 6 months of therapy with ruxolitinib. Eligibility criteria includes adult subjects with chronic GVHD and skin, joint and/or fascia sclerosis, who have received systemic corticosteroids for >12 months and at least one additional line of therapy OR systemic corticosteroids and at least two additional lines of therapy for chronic GVHD. A sample size of 47 subjects dosed (42 evaluable subjects and estimated 10% dropout) will allow an α of 0.044 and a power of 84% to test the null hypothesis response rate of 25% compared to an alternative of 45%. Subjects will receive ruxolitinib for 6 months for the treatment of sclerotic chronic GVHD. Subjects will be evaluated for GVHD status as well as non-relapse mortality, relapse of underlying malignancy and quality of life/functional status. Plasma cytokine levels and T/NK cell subset in peripheral blood will be measured at various time points. The response rate will be reported as a proportion and 95% exact confidence interval. If positive, the trial results will support other ongoing studies to establish the role of ruxolitinib in chronic GVHD in general and specifically in sclerotic chronic GVHD.

Study Schema

Patients with chronic graft-versus-host-disease and skin, joint and/or fascia sclerosis, who have received systemic corticosteroids for >12 months and at least one additional line of therapy OR systemic corticosteroids and at least two additional lines of therapy

Informed consent and registration

Ruxolitinib therapy for 6 months

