A two-stage design is planned to test the null hypothesis that the overall response rate $p \leq 0.250$ versus the alternative that $p \geq 0.450$. The first stage will occur once 18 subjects have completed 6 months of treatment. If only 4 or fewer out of the 18 subjects respond at the end of 6 months of treatment, the trial will be stopped for futility. At stage two, an additional 24 subjects will be enrolled for a combined total of 42 from both stages. If only 15 or fewer respond out of 42 subjects at the end of stage two, then no further investigation is warranted. If 16 or more respond then further investigation is warranted. This design achieves 84% power with a significance level of 0.044. Retrospective studies (31, 32, 40) have demonstrated that ruxolitinib is well tolerated and effective in patients with steroid-refractory chronic graft-versus-host disease (GVHD) in general and sclerotic GVHD. Therefore, the accrual will not be put on hold for interim analysis.

To meet our statistical endpoints, a sample size of 42 is required; however, to account for dropout rate of approximately 10%, the study will dose 47 subjects.

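### The stated 84% power is that of the response rule alone; the mortality rule in 10.4 lowers the chance of a positive trial by an amount that depends on drug-related mortality

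*Combined protocol and SAP*

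**What the plan says.** The synopsis says that 42 evaluable subjects "will allow an α of 0.044 and a power of 84"%. Section 10.1 gives the rule behind this: the null response rate is 25% and the alternative 45%. The first look is futility only ("If only 4 or fewer out of the 18 subjects respond at the end of 6 months of treatment", the trial stops). The final criterion is "If only 15 or fewer respond out of 42 subjects at the end of stage two, then no further investigation is warranted", so 16 or more of 42 is positive. The section concludes: "This design achieves 84% power with a significance level of 0.044". Neither place attaches a condition to the 84%.

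Section 10.4 adds continuous monitoring of deaths judged possibly, probably or definitely related to the study drug, with a null rate of 10% and an alternative of 20%. It explains its error rate: "The sample size is too small to control alpha and power simultaneously, so alpha is 0.19 to allow for 80% power". On a crossing, "accrual will be terminated". Its operating characteristics give a stopping probability of 0.192 and an expected sample size of 41.1 at 10% mortality, rising to 0.795 and 22.9 at 20%. As background it states: "The risk of treatment-related mortality is 10-20% in patients with steroid refractory chronic GVHD".

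Neither section combines the two rules. The plan gives no efficacy criterion for a trial whose accrual ends short of 42.

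**The concern.** The 16-responder criterion is defined only at 42 subjects. A trial that stops accruing for mortality before then has no route to a positive result under the plan. A reader of the synopsis or 10.1 would take 16% as the chance that the trial fails to be positive when the true response rate is 45%. If drug-related mortality is at the 10% null of the monitoring rule, that chance is nearer 30%. The reader could work this out only by combining two sections that the plan keeps apart. What is at stake is how the design is described to those who judge it, not the conduct of the trial or its decision rules.

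**Working it through.** **Step 1. Reproduce the plan's figure.** Inputs from 10.1: stage 1 continues with 5 or more of 18; the trial is positive with 16 or more of 42; p = 0.45.

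Power = sum over x = 5 to 18 of P(Bin(18, 0.45) = x) × P(Bin(24, 0.45) ≥ 16 − x) = 0.8406.

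The 84% is reproduced with no mortality stop in the calculation.

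**Step 2. Product check from printed figures.** With 0.192 from the 10.4 table, and deaths and responses taken as independent: 0.8406 × (1 − 0.192) = 0.679. This counts every stop up to subject 47.

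**Step 3. Joint model.** Each subject has a drug-related death with probability d, a response with probability 0.45, or neither. Death is a non-response and stays in the denominator, as 10.1 defines the endpoint and the full analysis set. The mortality boundary is applied after each subject up to subject 42, the futility rule at 18 and the final rule at 42. A mortality stop counts as not positive. Deaths are counted at once, as a boundary indexed by subject number implies.

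The printed boundary does not reproduce the printed operating characteristics (step 4), so a matched boundary is needed. At each look k from 3 to 47, stop at the smallest count c with P(Bin(k, 0.10) ≥ c) ≤ 0.08. This gives a stopping probability of 0.192 with expected size 41.1 at 10% (printed 0.192 and 41.1), and 0.798 with 22.9 at 20% (printed 0.795 and 22.9).

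| Drug-related mortality | Probability of a positive trial at 45% response |
|---|---|
| 3% | 0.835 |
| 5% | 0.82 |
| 8% | 0.77 |
| 10% | 0.705 |
| 12% | 0.62 |
| 15% | 0.47 |
| 20% | 0.22 |

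At 10% the joint model exceeds the product for two reasons: trials with few deaths tend to have more responders, and stops after subject 42 are left out (0.18 by subject 42 against 0.192 by subject 47). The range at 10% is 0.68 to 0.71.

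**Step 4. The boundaries as printed.** The text of 10.4 stops when deaths exceed b_k; the line above the table stops when they equal or exceed it. The same joint model with the printed b_k gives:

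| Reading | P(stop) at 10% | Positive trial at 10% | Positive trial at 5% |
|---|---|---|---|
| Equal or exceed b_k | 0.366 | 0.56 | 0.77 |
| Exceed b_k | 0.149 | 0.74 | 0.83 |

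Neither reading returns 0.192. The table's caption also gives alpha as 0.05 where the text gives 0.19.

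**Step 5. Sensitivity to delayed deaths.** Assume 20 subjects a year (10.3) and deaths spread evenly over 6 months (an assumption). On the equal-or-exceed reading a simulation gives 0.69 at 10% mortality in place of 0.56, because more subjects are enrolled before deaths accumulate. This is still below 84%.

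**The case against.** The strongest reply is that 84% is not an error. It is attached to the response hypotheses and is right for them. Quoting efficacy power without a separate safety rule is common practice, and 10.4 prints its stopping probabilities openly. This stands: the point is a missing condition, not a wrong calculation. Stopping for drug-related deaths is also what the rule is for, so a mortality stop is not a type II error in the usual sense.

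The second reply concerns the rate. A reader might infer that the trial's real power is 70%, or lower still because 10.4 cites 10-20% mortality. The documents do not support a single figure of that kind. The 10-20% describes treatment-related mortality in steroid-refractory chronic GVHD, with citations to a trial of imatinib or rituximab and a study of rituximab. The rule counts only deaths related to the study drug. The retrospective ruxolitinib series in section 2.0 reports 97% six-month and 92.7% one-year survival. Near 3% mortality the joint figure is 0.835, a loss of about half a percentage point (0.8406 − 0.835). That evidence is retrospective and limited, but it means 10% cannot be presented as the expected rate. It remains the rate that the plan chose as its monitoring null.

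A reader might also infer that accrual could resume after a crossing, because one sentence of 10.4 speaks of halting accrual and another of terminating it. The halting sentence refers to the stopping rules below it, and no restart procedure appears. The two terms should be made one, but they do not establish a halt that can be lifted.

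Finally, the step 3 figures belong to a matched boundary that the protocol does not print. That is correct, so they illustrate the size of the effect and should not be pasted into the protocol.

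**Conclusion.** The point holds as a conditional one. The 84% is the power of the response rule given that mortality does not end accrual before 42 subjects, and the synopsis and 10.1 do not say so. At the plan's null drug-related mortality of 10%, the chance of a positive trial at 45% response is about 0.68 to 0.71 on the printed stopping probability. With the printed b_k it is 0.56 or 0.74, depending on the wording. At 3% to 5% mortality the matched boundary gives 0.835 to 0.82, which is little or no loss.

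These figures assume that death is a non-response, that a mortality stop is not positive and, except in step 5, that deaths are known at once. The joint figures also ignore dropout. If subjects drop out, more than 42 must be dosed to have 42 evaluable, so some stops between subjects 43 and 47 would matter as well; the product of 0.68, which counts all of them, covers this at 10%. No joint figure can be final until 10.4 agrees with itself.

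**What to change.** 1. In 10.4, before any joint figure is computed, reconcile the exceed and equal-or-exceed wordings, the alpha of 0.05 and of 0.19, and the boundary table with its operating characteristics. Use one term for the consequence of a crossing. Which version is intended is for the sponsor to settle.
2. In the synopsis and 10.1, restate 84% as the power of the two-stage response rule given no mortality stop before 42 subjects.
3. Add a short table of the joint probability of a positive trial at 45% response by drug-related mortality (for example 3%, 5%, 8%, 10%, 12%, 15% and 20%), computed with the reconciled boundaries and with the assumptions stated. Do not replace 84% with a single lower figure.

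The cost is some wording, one small table and a stated power that looks less favourable at higher mortality. It adds no patients, and the joint table itself requires no change to the clinical rule.

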11.1 Quality Assurance

Complete records must be maintained in a research chart on each subject treated on the protocol. Research chart can be maintained either as an electronic record, paper chart or a combination of both. These records should include primary documentation (e.g., laboratory report slips, physician notes, etc.) which confirm that:

- The subject met the eligibility criteria.
- Signed informed consent was obtained prior to treatment.
- Treatment was given according to protocol (dated notes about doses given and reasons for any dose modifications).
- Toxicity was assessed according to protocol (laboratory report slips, etc.).
- Response was assessed according to protocol (dated notes on clinical assessment, laboratory reports as appropriate).

